2.0 STUDY SYNOPSIS

Title of Study:	Immunologic Efficacy of Heplisav B Vaccine in Patients Undergoing Treatment with Immunosuppressive Medications
Sponsor:	Baylor Scott and White Research Institute
Phase of Development:	Phase 1 (Medically immunosuppressed subjects)
Objectives:	Preliminary trial of Heplisav-B vaccine in medically immunosuppressed patients with co-primary objectives of vaccine immunogenicity and patient safety
Study Design:	This is an open label exploratory study of the immunologic efficacy and safety of an FDA licensed HBV vaccine that contains HsAg-1018 adjuvant which has TLR 9 agonist properties (Heplisav-B). It will be used in patients treated with long term immunosuppressive drug therapy. The patients will be given two doses of Heplisav-B, the first delivered at the baseline visit and the second at week 4. Anti-HBs titers will be determined at baseline and at weeks 4, 8, 12, 24 and 60. The proportion of those with seroprotective anti-HBs levels and the geometric mean titers of anti-HBs at each time interval will be compared with those observed in phase III trials of immunocompetent individuals receiving the same dosing schedule. Individuals who fail to demonstrate protective levels of anti-HBs at week 8 will be given a third booster dose at week 12.
Study Population:	A total of 18 patients will be entered into the study including 3 evenly sized groups of 6 as follows: Group A patients are taking tumor necrosis factor alpha or interleukin inhibitor therapy for underlying chronic inflammatory disorders; Group B patients are taking chemotherapy for solid organ malignancy; and Group C patients are either recipients of livers from anti-HBc positive donors or individuals transplanted for chronic HBV infection without recurrent hepatitis B at the time of enrollment. Serologic Characteristics Per Group: All patients in Groups A and B must be HBsAg negative but anti-HBc positive to qualify indicating that they have serologic evidence for resolved hepatitis B. Those with low titer (<20 mIU) antibody will not be specifically excluded permitting observation of a possible anamnestic anti-HBs response. Patients in Group C will have either a remote history of liver transplant for HBV or receipt of an anti-HBc positive donor liver. Eligibility requires HBsAg to be negative w/wo anti-HBc reactivity.

Safety Evaluation:	Yes
Efficacy Evaluation:	Yes
Schedule of Events:	In the absence of appropriate documentation, all patients will initially be screened for HBsAg, anti-HBc, and anti-HBs status by qualitative testing at a screening visit. Patients in Group A and B found to be anti-HBs positive will be tested for anti-HBs quant within one week to confirm final eligibility. Two doses of Heplisav-B will be administered at a baseline visit and 4 weeks later. Anti-HBs levels will be assessed at the baseline visit and again at weeks 4, 8, 12, 24 and 60. All patients who fail to respond with seroprotective anti-HBs levels (≥ 10 mIU/mL) at week 8 will be given a third dose of vaccine at week 12 and followed until week 60. Liver transplant patients (Group C) will be vaccinated and followed in the same manner as Groups A and B.

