5.0. TRIAL OBJECTIVES

There are two co- primary objectives: (1.) To assess immunogenicity of Heplisav-B and (2.) to assess safety in medically immunosuppressed patients. The former will require assessing the proportion of patients who respond with seroprotective levels (>10 mIU/mI) of anti-HBs and who maintain this response until study completion at week 60. The second objective will require follow up of all patients for one year after the last dose of vaccine during which time all adverse events will be collected.

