10.1 Safety Endpoints

Patient safety is a co-primary objective of the study and the following endpoints will be considered and used for future reporting:

- 1. Proportion of subjects with unsolicited AEs after inoculation. All adverse events including those that are unsolicited will be recorded for a period of 28 days after vaccine administration, and at each visit changes in the patient's state of health will be recorded on the Appendix 1 (AE capture form) and as needed on the Appendix 2 form. To facilitate accurate reporting in real time, patients will be questioned at a weekly telephone assessment and seen by the principal investigator should this appear warranted. Photographic evidence by the patient may be requested between visits for certain AEs.
- 2. Proportion of subjects with SAEs. The study will capture all SAEs (and Grade 3 AEs) that occur through one year after the last dose of vaccine. To facilitate accurate reporting, all patients with these events will be seen within 48 to 72 hours and acted upon if needed. Follow up will continue until at least 52 weeks after the last dose of vaccination Data will be collected on the Appendix 1 safety form and in the case of Group A, Appendix 2 as well.
- 3. Proportion of subjects with MAAEs. All MAAEs that occur within one year of the last vaccine dose will be captured. Patients will be handled as in 2 Above.
- 4. Proportion of subjects with pIMMCs. This will be captured for a period of 52 weeks after the last dose of vaccine. Patients will be handled as in 2 and 3 above. Data will be reported on both the Appendix 1 and Appendix 2 safety forms.
- 5. Proportion needing an increase in immune suppressive medication. All concomitant medications used during the 28 day period following vaccination and those used to treat MMAEs or SAEs during a 12 month period after the last dose of vaccine will be recorded. Special attention will be given to new or dose adjusted immune suppressive medications that are needed to treat adverse events. Data will be captured in Appendix 1 (adverse event capture form) under the header "Type Intervention."

10.2 Further Safety Considerations:

- a. C-reactive protein blood testing will be used to assess augmentation of inflammatory disease activity in Group A.

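### Patients given the third dose at week 12 have 48 weeks of scheduled follow-up, but the safety objective and four safety endpoints require a year after the last dose

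*Protocol*

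**What the plan says.** **Where follow-up ends.** The Synopsis (Schedule of Events) says that patients without seroprotective anti-HBs at week 8 "will be given a third dose of vaccine at week 12 and followed until week 60". Section 5.0 describes responders as those who "maintain this response until study completion at week 60". The last column of Table 1 is Visit 7 at week 60, plus or minus one week. Section 7.3 also treats week 60 as the end of the study when it describes continued safety collection.

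**What safety follow-up requires.** Section 5.0 also states: "The second objective will require follow up of all patients for one year after the last dose of vaccine". Four of the five endpoints in section 10.1 have the same horizon:

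- Item 2 (SAEs and Grade 3 AEs): "The study will capture all SAEs (and Grade 3 AEs) that occur through one year after the last dose of vaccine", and "Follow up will continue until at least 52 weeks after the last dose of vaccination".
- Item 3 (MAAEs): "All MAAEs that occur within one year of the last vaccine dose will be captured".
- Item 4 (pIMMCs): "This will be captured for a period of 52 weeks after the last dose of vaccine".
- Item 5 (increase in immunosuppression): medication used to treat medically attended or serious events "during a 12 month period after the last dose of vaccine will be recorded".

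Item 1, unsolicited AEs, uses 28 days and is not affected.

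**Related places.** Section 6.6 gives a 52-week observation period but refers only to two doses. Sections 7.5, 10.7 and 11.4 and the Appendix 3 table repeat the 52 weeks after the last dose for the patients they cover. Section 10.3 (pregnancy) and an Appendix 3 footnote stop at week 60.

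**The concern.** Week 60 fits a two-dose schedule. The optional third dose moves the last dose from week 4 to week 12, and the end of the visit schedule does not move with it. A site that follows Table 1 exactly would not deliver the follow-up that section 5.0 demands of all patients.

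Safety is a co-primary objective. The uncovered weeks fall only on patients who received the most vaccine, and the third dose is a planned branch: the proportion needing it is a secondary endpoint in section 6.1. If the schedule is followed as written, safety proportions described as one-year or 52-week would pool patients with 56 scheduled weeks after their last dose and patients with 48.

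**Working it through.** The check is calendar arithmetic, with day 0 as dose 1 and 52 weeks = 364 days.

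**Inputs.** Dose 2 at week 4 and dose 3 at week 12 (Synopsis, section 4.7). Last visit at week 60, plus or minus 7 days (Table 1, section 4.7). Week-12 window: up to 5 days either side in Table 1, 7 days in section 4.7. Week-4 window: up to 5 days (Table 1). Calls: weekly for 4 weeks after each dose (Table 1 footnote). Missed visits: re-booked within 3 to 5 working days (section 8.3).

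**Nominal follow-up** = week of last visit − week of last dose.

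| Last dose | Scheduled follow-up | 52-week point | Against week 60 |
|---|---|---|---|
| Dose 1, week 0 | 60 − 0 = 60 weeks | week 52 | covered, 8 weeks to spare |
| Dose 2, week 4 | 60 − 4 = 56 weeks | week 56 | covered, 4 weeks to spare |
| Dose 3, week 12 | 60 − 12 = 48 weeks | 12 + 52 = week 64 | 4 weeks short (4/52 = 7.7%) |

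The one-dose row arises because section 4.7 withholds dose 2 if the titer is already 300 mIU/ml or more.

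**Do the visit windows close the gap?** The requirement is 364 days.

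- Table 1 windows (week 12 = days 79 to 89; week 60 = days 413 to 427): shortest 413 − 89 = 324 days (46.3 weeks); longest 427 − 79 = 348 days (49.7 weeks).
- Section 4.7 windows (week 12 = days 77 to 91): shortest 413 − 91 = 322 days (46.0 weeks); longest 427 − 77 = 350 days (50.0 weeks).
- One section 8.3 re-booking, assumed to add about 7 calendar days at the edge of the window: week 60 moved to day 434 gives 434 − 77 = 357 days (51.0 weeks); week 12 moved to day 98 gives 413 − 98 = 315 days (45.0 weeks).

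None reaches 364. Section 4.7 sets no firm cap on deferral for intercurrent illness, so 51 weeks is not an absolute limit, but the schedule does not provide more.

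**Two-dose patients.** Week 4 = days 23 to 33: 413 − 33 = 380 days (54.3 weeks) to 427 − 23 = 404 days (57.7 weeks). With week 4 re-booked to day 40: 413 − 40 = 373 days (53.3 weeks). All exceed 364.

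**Telephone calls.** The calls after dose 3 end at about 12 + 4 = week 16, so they do not reach weeks 60 to 64.

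**Upper bound on the loss.** If all 18 patients needed dose 3: 18 × 4 = 72 patient-weeks out of 18 × 52 = 936 required, again 7.7%. This is a ceiling; the number of third-dose recipients is unknown.

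**The case against.** The strongest reply is that the obligation is already written. Sections 5.0 and 10.1 state the one-year requirement, and item 2 says at least 52 weeks, so an unscheduled contact or a call log could meet it. Sections 10.1 and 10.7 also provide visits within 48 to 72 hours of a serious or Grade 3 event, and section 10.7 follows such events to resolution. Events that begin before the week-60 visit would therefore be followed through. The trial is exploratory and descriptive with 18 patients, nobody may need a third dose, and no hypothesis test rests on weeks 60 to 64.

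Part of this stands. It narrows the gap to events with onset between about week 60 and week 64 in third-dose recipients, and it limits how serious the point is. Section 6.6 is also silent on the third dose rather than wrong.

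It does not remove the contradiction. Event-triggered visits happen only once an event is known; they neither find unreported events nor confirm that none occurred. Week 60 cannot be read as the end of immunogenicity follow-up alone, because section 7.3 uses it for safety data too. Appendix 3 shows the conflict directly: for a related Grade 3 AE or SAE, the table row gives 52 weeks after the last dose and its footnote gives week 60. Those differ in practice once a third dose has been given. An analysis plan could not repair this, since it cannot add a patient contact.

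**Conclusion.** The concern holds and should be fixed. For third-dose recipients the schedule provides 48 weeks after the last dose against a stated 52, and no combination of stated visit windows gives more than 50.0. New events in about the last 4 weeks of the safety window have no scheduled ascertainment. Subject to the uncapped illness deferrals in section 4.7, one- and two-dose patients are covered.

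The conclusion rests on the text and Table 1. The drawing of Figure 1 is not available, but the Synopsis, sections 5.0 and 7.3 and Table 1 all end at week 60. The 7-day re-booking is an assumption and does not alter the result. The number of patients affected lies between 0 and 18.

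**What to change.** Reconcile the week-60 passages with those that count from the last dose. Two routes are open.

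1. **Keep the 52 weeks.** Add to Table 1, for third-dose recipients only, a safety contact no earlier than 364 days after the actual date of dose 3, its mode left to the sponsor. Nominally this is week 64. Under the section 4.7 window for dose 3 it falls between 77 + 364 = day 441 (week 63) and 91 + 364 = day 455 (week 65), so tie it to the dose date rather than to a fixed week. Align the Synopsis, sections 5.0 and 6.6, and the week-60 wording in sections 7.3 and 10.3 and the Appendix 3 footnote. The cost is one extra contact per third-dose recipient, 0 to 18 in all.
2. **Keep week 60.** Restate the safety window for third-dose recipients as follow-up to the week-60 visit, about 48 weeks after the last dose, in sections 5.0 and 10.1 (items 2 to 5) and wherever 52 weeks is repeated (sections 7.5, 10.7, 11.4 and the Appendix 3 table). Leave the window unchanged for other patients, and report the four proportions with actual follow-up time by number of doses. The cost is wording only.

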3.0 LIST OF ABBREVIATIONS

Abbreviation or Term	Definition/Explanation
AE	Adverse Event
ALT (SGPT)	Alanine aminotransferase (Serum Glutamic Pyruvic Transaminase)
AST (SGOT)	Aspartate aminotransferase (Serum Glutamic Oxaloacetic Transaminase)
IRB	Institutional Review Board
μg	Microgram
MAAE	Medically attended adverse event
mL	Milliliter
PE	Physical examination
piMMCs	Potentially immune-mediated medical conditions
SAE	Serious Adverse Event
SGOT (AST)	Serum Glutamic Oxaloacetic Transaminase
SGPT (ALT)	Serum Glutamic Pyruvic Transaminase
NsCap	HBsAg negative, anti-HBc positive
ISDT	Immunosuppressive drug therapy
HBV	Hepatitis B virus
HBVr	Hepatitis B virus reactivation
HBIg	Hepatitis B immune globulin
HBsAg-1018	Vaccine adjuvant for Heplisav-B

4.0. BACKGROUND

Hepatitis B vaccination is recommended for all immunocompromised persons at risk for hepatitis B infection. However, traditional recombinant HBV vaccines have limited efficacy in this situation even when given in higher dosage. In addition, the relatively cumbersome 3 dose regimen with traditional HBV vaccines has been associated with disappointingly low rates of vaccine completion.

Recently, the Food and Drug Administration has licensed a new HBV vaccine (Heplisav-B®) which incorporates HBsAg particles bound to 1018 immunostimulatory sequence which serves as a TLR 9 agonist. The incorporation of the HBsAg-1018 adjuvant makes the vaccine considerably more immunogenic than traditional HBV vaccines that contain a solid phase alum adjuvant. In addition, Heplisav-B offers the advantage of only requiring two doses given at 0 time and 4 weeks later. This vaccine stimulates a directed immune response to hepatitis B surface antigen (HBsAg) instead of the multi-pathway, broad immunostimulatory response induced by alum adjuvant. Two randomized controlled clinical trials in immunocompetent adults and a third randomized, controlled study in patients with chronic kidney failure have shown Heplisav-B to be considerably more immunogenic when compared to a traditional recombinant vaccine (Engerix®).5-8 Heplisav-B given in two doses 4 weeks apart induced significantly higher seroprotection (anti-HBs ≥ than 10 miU/ml) rates when compared to Engerix given in a 3 dose regimen at 0, 4 weeks and 24 weeks. Increased immunogenicity was evident by 8 weeks after the second dose of Heplisav-B. Also, geometric mean titers of anti-HBs were significantly greater with Heplisav-B doses starting at week 12. In a randomized, controlled trial in patients with chronic kidney failure, a group that demonstrates attenuated responses to traditional vaccine, patients were randomized to 3 injections of Heplisav-B or to Engerix given in a double dosage at four intervals. seroprotection rates were only slightly higher in the Heplisav-B group (89% vs 81.9%), geometric mean titers of anti-HBs were significantly higher in the Heplisav-B group (587 miU/ml versus 156 miU/mL) by week 28.

It is important to note that adverse event profiles did not differ between the vaccines used in these studies.⁵⁻⁸ One case of granulomatosis with polyangitis was reported 170 days after the second dose in the Heplisav B group but the collective data from these trials demonstrated that the vaccine did not induce autoimmune disorders at a higher than expected frequency (Dynavax Technologies, data on file) Moreover, the frequencies and titers of ANA and anti-dsDNA were comparable in the two vaccine treatment groups in these studies.

Potential Clinical Utility of a More Immunogenic HBV Vaccine

The development of a more immunogenic vaccine that induces rapid protection against HBV has particular relevance in situations where timely induction of neutralizing anti-HBs is desirable and

whenever attenuated responses to traditional HBV vaccine may otherwise be anticipated. Both of these issues are relevant in patients who are immunosuppressed due to medication. This is especially relevant in patients with resolved hepatitis B due to long term persistence of the genomic template for viral transcription in liver tissue and an inherent risk that hepatitis B viral reactivation may occur when immunosuppressed (see 1, below).

Thus, this protocol is an exploratory trial to assess the safety and effectiveness of Heplisav-B in three common clinical situations where patients are medically immunosuppressed: (1) in patients given tumor necrosis factor (TNF) or interleukin inhibitor therapy for chronic inflammatory disorders; (2) in patients placed on cancer chemotherapy for solid organ malignancy; and (3) in patients who are immunosuppressed after liver transplantation either done for a) chronic hepatitis B or for b) the same or other indications during which they receive a liver from an anti-HBc positive donor.

1. Hepatitis B reactivation. Hepatitis B reactivation (HBVr) is defined by a sudden increase in HBV DNA and ALT/AST level, and is most frequently caused by immunosuppressive drug therapy (ISDT) where it is thought to occur because of a loss of immunologic control over HBV replication. Many cases of HBVr are subclinical or mild, but it also can be severe enough to cause liver failure. Hepatitis B reactivation during ISDT not only occurs in HBsAg-positive patients but also in those who are HBsAg negative yet anti-HBc positive.⁹ This is a serologic profile that is typically observed in cases of resolved hepatitis B. As many as 60 to 80% of anti-HBc positive persons have detectable anti-HBs_and this has been associated with a reduced rate of HBVr in several observational studies of HBsAg negative, anti-HBc patients treated with ISDT.⁹

Current management recommendations to reduce the risk of HBVr in HBsAg negative/anti-HBc positive patients during ISDT vary depending on the immunologic potency of the drug(s) used and the serologic profile of the patient. It is currently recommended that persons with resolved hepatitis B who are taking tumor necrosis factor or interleukin inhibitor either receive prophylactic antiviral therapy or close monitoring of aminotransferase and HBV DNA levels. This dichotomous recommendation Is based on data collected from large observational studies showing a relatively low rate (0 to 5%) of HBVr when anti-HBc positive patients take these biologic agents without anti-HBV prophylaxis.¹² In contrast, anti-HBc positive patients undergoing cancer chemotherapy are considerably more likely to reactivate (10 to 20%), and standard recommendations call for antiviral prophylaxis during chemotherapy and for as long as 12 months after discontinuation if rituximab or other B cell depleting agents are used.^{10,11}

The protective role of neutralizing anti-HBs has not been well defined in patients receiving ISDT. However, there are indications that high titers of anti-HBs may be helpful in preventing reactivation during cancer chemotherapy. In one observational study it was found that patients with non Hodgkin's lymphoma who had anti-HBs titers >100 mIU failed to demonstrate HBV

reactivation during CHOP combined with B cell depletion therapy whereas those with lower anti-HBs titers frequently did.¹³ Furthermore, a more recent meta-analysis of 20 studies of resolved hepatitis B patients with hematologic malignancy documented that anti-HBs positivity was associated with reduced HBVr risk (pooled odds ratio of 0.21) when compared to resolved cases who lacked anti-HBs. Unfortunately, qualitative rather than quantitative assessments of anti-HBs have been used in the vast majority of studies which makes it difficult to assess the relationship between anti-HBs concentration and protection against HBV reactivation or the protective benefit of periodic booster dosing in the transplant setting.¹⁴ (See section 2, below).

- 2. De novo hepatitis B after liver transplantation. The use of cadaveric (or living) donors harvested from individuals found to be negative for HBsAg but positive for anti-HBc has become a standard practice due to the urgent need for an expanded donor pool. De novo HBV infection in HBV susceptible recipients of these organs occurs in more than of 50% of cases if not given antiviral prophylaxis. Such patients are generally treated with long-term antiviral prophylaxis which is sometimes combined with peri-operative hepatitis B immune globulin. The concentration of anti-HBs that would be partially protective against de novo hepatitis B in this setting has not been defined. However, recent studies using multiple booster doses of HBV vaccine have reported successful termination of HBIg and long term antiviral prophylaxis in recipients of anti-HBc-positive livers provided they develop sustained anti-HBs titers greater than 100 mIU/mI.¹⁷
- 3. Prevention of recurrent hepatitis B after liver transplantation. Patients transplanted for chronic HBV infection are treated_with hepatitis B immune globulin (HBIg) for variable periods along with a third generation nucleoside analogue with anti-HBV potency to prevent recurrence of HBsAg, HBV DNA, and overt hepatitis B. The nucleoside analogue therapy must be given indefinitely. HBIg contains high titers of anti-HBs and serum anti-HBs concentrations of 100 miU/ml or greater were shown to be partially effective in the prevention of recurrent hepatitis B before nucleoside analogue therapy was developed. Attempts to vaccinate such patients in preparation for transplantation often fail due to the immune suppression effect of end stage liver disease, the requirement for a second or third dose in patients with short waiting times, and because transplant recipients are immunosuppressed after surgery with tacrolimus, mycophenolate, rapamycin or other anti-rejection therapies.

Why is this Study Being Done? Rationale/Significance of Proposed Study In Selected Patient Groups Receiving Immunosuppressive Drug Therapy

Chronic ISDT results in an attenuated antibody response to new and repeat antigen exposure. B cell depletion therapy further results in rapid attrition of pre-existing anti-HBs. Weakened antibody responses to HBV vaccine during ISDT can be important factors when trying to protect a patient with resolved hepatitis B from HBVr or in preventing recurrent or de novo hepatitis B

after liver transplantation. The proposed study is the first known to the investigator in which patients are administered HBsAg-1018 containing vaccine immediately before or during ISDT. It is also the first to use this vaccine in persons with serologic evidence for resolved hepatitis B. However, vaccinating anti-HBc positive patients who are taking ISDT can be justified by previously published studies. First, as many as 40% of patients with the serologic profile of resolved hepatitis have seroprotective levels of anti-HBs due to the fact that exposure to HBV may have occurred remotely in the past. Second, an anamnestic boost in anti-HBs has been reported in a substantial minority of immunocompetent anti-HBc positive individuals after a single dose of traditional HBV vaccine. In consideration of these findings, the current study will not exclude anti-HBc positive patients who have weak anti-HBs levels (<20 mIU/ml). Third, the medical literature supports a lower frequency of HBVr in anti-HBs positive individuals over a broad range of ISDTs. Pourth, some studies using quantitative anti-HBs assays have reported greater protection against HBVr in persons having a high anti-HBs titer compared to individuals with low titer or no detectable anti-HBs.

Heplisav-B vaccine has been shown to more quickly result in seroprotective levels of anti-HBs and higher geometric mean titers than traditional HBV vaccine in immunocompetent recipients including the elderly, persons with diabetes mellitus, and patients with chronic kidney failure. These are important groups to have studied because It can be anticipated that some recipients may have had age or disease-related subclinical immune deficiency.

Use of Heplisav-B in patients with prior hepatitis B (Groups A and B).

Prevention of HBVr.

It is the opinion of the investigator that the immunologic efficacy of Heplisav-B in patients with resolved hepatitis B is an extremely important clinical area to study because it offers the potential to change current management recommendations for the prevention of HBVr during ISDT.¹⁹ This is very relevant in (a) persons undergoing immunosuppressive treatment for chronic inflammatory disorders which are considered to be autoimmune in nature and b) individuals who are undergoing treatment with cancer chemotherapy where the risk of HBVr is particularly high due to the higher level of immune suppression. Further insight into the clinical relevance of a more immunogenic vaccine to prevent HBVr during ISDT in these two groups is provided below.

1. Group A (chronic inflammatory disorders). A rapid and highly effective response to vaccination might supplant any concern about the need for antiviral therapy in patients treated with tumor necrosis factor or interleukin inhibitor therapy for chronic rheumatic, intestinal or dermatologic disorders. Taken together this is a large patient population with current estimates of use for TNF inhibitor therapy being 3 million people in the United States. Major quality of life improvement may occur using TNF inhibitor therapy but this often requires the

use of long-term ISDT. This indefinite exposure to ISDT can put the patient at prolonged risk of HBVr. At the current time routine antiviral prophylaxis is not recommended in this setting because HBVr rates are quite variable in the literature and anti-HBV prophylaxis would have to be given indefinitely. ¹⁹

- **2. Group B (cancer chemotherapy).** The rapid induction of high titer anti-HBs following vaccination with Heplisav-B either delivered prior to or soon after starting chemotherapy could prove helpful in preventing HBVr in resolved hepatitis B patients treated for solid organ malignancy. Such patients have the highest risk for HBVr when compared with the other groups (A and C) proposed in this study. Reactivation frequency varies from 10 to 20% for anthracycline based chemotherapy and 20 to 50% for lymphoma therapy that includes rituximab. The demonstration of high titers of anti-HBs with Heplisav-B during cancer chemotherapy would be a significant breakthrough because anti-HBs levels \geq 100 mIU/ml have been shown to be associated with significantly lower rates of HBVr during rituximab treatment. 9,13
- 3. Group C: susceptible recipients of anti-HBc-positive livers. Until recently, HBV susceptible recipients of cadaveric liver donations were routinely vaccinated for hepatitis B at Baylor Scott and White and other programs throughout the United States. In part, this was done because of the possibility that a high MELD score recipient might acquire an organ from an anti-HBc positive donor. Vaccination completion was often not completed, however, prior to transplant and the use of HBlg and long term antiviral prophylaxis ultimately made de novo hepatitis B a treatable condition. To prevent de novo infection, however, requires indefinite antiviral prophylaxis, possibly life long. Should Heplisav-B induce high anti-HBs titers in these immune suppressed patients, it could limit antiviral drug exposure by deploying a periodic booster dose strategy.¹⁷

Group C: patients transplanted for chronic hepatitis B. These patients currently are treated with short duration HBIg and life-long antiviral prophylaxis. All continue to take anti-rejection therapy indefinitely. Hepatitis B vaccine is not used in these patients prior to transplant. Frequent double dose inoculations of HBV vaccine post transplant have been given in clinical trials in an attempt to eliminate antiviral therapy in highly selected patient groups. However, most studies have failed to reliably induce protective anti-HBs titers with a few notable exceptions.²⁰ Patients with successful prophylaxis remain HBsAg negative, anti-HBc positive, and HBV DNA negative (similar to resolved cases of hepatitis B), but anti-HBs is almost always non detectable after liver transplantation for hepatitis B. This suggests that patients without recurrent hepatitis B might be at continued risk for recurrence if antiviral therapy were to be withdrawn. It would be instructive to see if high levels (>100 mIU/mI) of protective anti-HBs could reliably be induced in these patients using a routine booster dose strategy and if this could lessen the requirement for life long antiviral treatment.

